## **15 Appendix 2: Treatment guidelines for hyperkalemia**

### **(serum potassium greater than or equal to 5.3 mmol/L)**

#### **General principles**

Elevation of potassium levels above the predefined values should be repeated and confirmed before any action is taken. Any patient who experiences a potassium level 5.5 mmol/L confirmed by repeated testing during the screening period should be withdrawn from the study. Any patient with a serum potassium > 5.3 mmol/L after randomization requires regular, repeated checks of potassium concentration (beyond that prescribed in the protocol) until it is clear that the potassium concentration is stable and not rising into the range of concern (5.5 and < 6.0 mmol/L) or potential danger (6.0 mmol/L).

Investigators should not randomize a patient with a serum potassium 5.5 mmol/L during the screening period. Patients with elevated potassium value will be managed according to the corrective actions outlined below.

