**Exclusion criteria**

1. Previous history of myocardial infarction or chronic heart failure
2. Previous PCI, coronary artery bypass graft (CABG), implantation of other heart assist devices or heart transplantation
3. Known history of angioedema
4. Previous history of intolerance to recommended target doses of ACEIs or ARBs.
5. Previous use of sacubitril/valsartan
6. History of hypersensitivity or contraindications to the study drugs including ACEI, ARB, sacubitril/valsartan
7. Symptomatic hypotension and/or a SBP  $< 100$  mmHg at Visit 1 (screening), Visit 2 (randomization), Visit 3 (outpatient dose titration) or Visit 4 (follow-up)
8. Estimated GFR  $< 30$  mL/min/1.73m^2 as measured by the simplified MDRD formula at Visit 1 (screening), Visit 2 (randomization), Visit 3 (outpatient dose titration) or Visit 4 (follow-up) or  $> 25\%$  decline in eGFR between Visit 1 and Visit 2 or between Visit 2 and Visit 3 or between Visit 3 and Visit 4
10. Serum potassium  $> 5.2$  mmol/L at Visit 1 (screening), Visit 2 (randomization), Visit 3 (outpatient dose titration) or Visit 4 (follow-up)
11. History of severe pulmonary disease
12. Diagnosis of peripartum or chemotherapy induced cardiomyopathy prior to Visit 1
13. Documented untreated ventricular arrhythmia with syncopal episodes within the 3 months prior to Visit 1
14. Symptomatic bradycardia or second or third degree heart block without a pacemaker
15. Presence of hemodynamically significant mitral and/or aortic valve disease, except mitral regurgitation secondary to left ventricular dilatation
16. Presence of other hemodynamically significant obstructive lesions of left ventricular outflow tract, including aortic and sub-aortic stenosis
17. Life expectancy is less than 1 year
18. Any surgical or medical condition which might significantly alter the absorption, distribution, metabolism, or excretion of study drugs, including but not limited to any of the following
  - History of active inflammatory bowel disease during the 12 months before Visit 1.
  - Current duodenal or gastric ulcers during the 3 months prior to Visit 1
  - Evidence of hepatic disease as determined by any one of the following: AST or ALT values exceeding 2 x ULN at Visit 1, history of hepatic encephalopathy, history of esophageal varices, or history of portacaval shunt
  - Active treatment with cholestyramine or colestipol resins

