## **4.2 Study visits**

### **4.2.1 Screening**

#### **Visit 1 (Screening Visit)**

All patients must provide informed consent before any study-specific procedure is performed. At Visit 1, patients' eligibility for entering the randomization period, including whether the patient's vital signs are stable after PCI, will be assessed by the investigator. Whether enalapril is included in the medicine used immediately after the operation. Screening potassium levels and eGFR will be assessed by sending blood samples to the central laboratory and only patients with the required values per the entry criteria will be eligible for entering the randomization period, which will begin at Visit 2.

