### **4.2.2 Randomization**

#### **Visit 2 (Randomization Visit)**

Patients who have met all the inclusion criteria and none of the exclusion criteria at the end of the screening period will be randomized to either enalapril or sacubitril/valsartan in a 1:1 ratio. Patients randomized to enalapril continue to receive enalapril, while

patients randomized to sacubitril/valsartan discontinue enalapril to ensure a minimum 36-hour washout period prior to initiation of ARNi therapy. The first dose of sacubitril/valsartan is followed by 6 hours of monitoring for hypotension. After the condition is stable, patients can be discharged from the hospital at any point in time at the discretion of the clinician-investigator. The starting dose during the in-hospital initiation phase is selected using a dose titration algorithm based on systolic blood pressure (SBP) (Figure 1).

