#### **7.5.4.3 Potassium and eGFR assessments**

In addition to the central laboratory assessments, potassium and eGFR, may be measured locally during the screening period (Visit 1), up to the randomization visit (Visit 2) to determine eligibility of the patient into the trial. potassium and eGFR measurements may also be performed during the outpatient dose titration and follow-up period, mainly at the unscheduled visits, to monitor the tolerability to study medication dose administered and adjust medication dose if needed.

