## **12 Protocol adherence**

Investigators ascertain they will apply due diligence to avoid protocol deviations. Under no circumstances should the investigator request approval of a protocol deviation, as no authorized deviations are permitted. If the investigator feels a protocol deviation would improve the conduct of the study this must be considered a protocol amendment, and unless such an amendment is agreed upon by research team and approved by the Ethics Committee of the Second Affiliated Hospital of Nanchang University it cannot be implemented.

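### Appendix 2 twice gives 5.5 mmol/L as the screening potassium limit, while exclusion criterion 10, which governs entry, excludes values above 5.2 mmol/L

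*Protocol*

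**What the plan says.** Exclusion criterion 10 reads the same in the Protocol synopsis and in section 5.2: "Serum potassium $> 5.2$ mmol/L at Visit 1 (screening), Visit 2 (randomization". It goes on to name Visits 3 and 4, which are not at issue here.

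Two sections say how that criterion is used. Section 4.2.1 (Screening) states, for potassium and eGFR, that "only patients with the required values per the entry criteria will be eligible for entering the randomization period". Section 4.2.2 (Randomization) requires that patients meet all inclusion criteria and "none of the exclusion criteria at the end of the screening period will be randomized".

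Appendix 2, General principles, sets a screening limit in two sentences, both with the figure 5.5 mmol/L. The first says that a patient at that level, "confirmed by repeated testing during the screening period should be withdrawn from the study". The second is addressed to the randomization decision itself: "Investigators should not randomize a patient with a serum potassium 5.5 mmol/L during the screening period".

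Section 7.5.4.3 adds, for both of these laboratory values, that they "may be measured locally during the screening period (Visit 1), up to the randomization visit (Visit 2) to determine eligibility of the patient". These local tests come on top of the central laboratory assessments.

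**The concern.** One eligibility decision should have one number. Here the criterion says above 5.2 mmol/L, and the appendix on high potassium says 5.5 mmol/L for the same period and the same decision. Potassium may be measured locally up to Visit 2 to settle eligibility, so the person judging a result may look up the limit, and the hyperkalemia appendix is a natural place to look. Someone who takes it from there could accept a value of 5.3 or 5.4 mmol/L that the entry criteria exclude.

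At stake is the entry of a patient with raised potassium into a trial of two drugs that act on the renin-angiotensin system, in which hyperkalemia is a listed safety outcome (sections 1 and 10.5). The point concerns eligibility and safety only, not inference.

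**Working it through.** The plan has no calculated figure to reproduce. The check sets the stated limits side by side.

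**Inputs**
- Criterion 10 (synopsis and section 5.2): excluded if potassium is above 5.2 mmol/L at Visit 1 or Visit 2.
- Appendix 2, General principles, first screening sentence: withdraw at 5.5 mmol/L if confirmed.
- Appendix 2, General principles, second screening sentence: do not randomize at 5.5 mmol/L.
- The comparison sign before 5.5 is not visible in either Appendix 2 sentence. That is probably a loss in reading the PDF and is not counted as an error. Both plausible signs are tried below.

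**Step 1: difference between the limits.** 5.5 − 5.2 = 0.3 mmol/L. The limit is stated in four places: two give 5.2 and two give 5.5.

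**Step 2: classification of values.** This assumes reporting to one decimal, the precision in which the protocol writes its limits.

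| Potassium (mmol/L) | Criterion 10 | Appendix 2 if the sign is ≥ | Appendix 2 if the sign is > |
|---|---|---|---|
| 5.2 | not excluded | not stopped | not stopped |
| 5.3 | excluded | not stopped | not stopped |
| 5.4 | excluded | not stopped | not stopped |
| 5.5 | excluded | stopped | not stopped |
| 5.6 | excluded | stopped | stopped |

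With ≥ the gap is {5.3, 5.4}. With > it is {5.3, 5.4, 5.5}. The values common to both are 5.3 and 5.4, so the discrepancy does not depend on the missing sign. The value 5.5 would join only under >, which cannot be seen and is not claimed.

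**Step 3: which figure governs.** Section 4.2.1 makes the entry criteria decide whether a potassium value is acceptable, and section 4.2.2 allows randomization only when no exclusion criterion is met. Criterion 10 is an exclusion criterion and names both visits. The figure out of line is therefore the 5.5 in Appendix 2.

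**Step 4: whether the two rules can both be obeyed.** Every value that Appendix 2 stops is also excluded by criterion 10, so the Appendix 2 rule lies inside the stricter one. Once criterion 10 is applied, the 5.5 sentences stop nobody further. Their only remaining effect is to suggest a looser cut-off.

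**The case against.** The best case for leaving the text alone has four parts.

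- **The rules are nested.** Both can be obeyed at once, and no sentence in Appendix 2 says that 5.3 or 5.4 mmol/L is acceptable. This stands. A reader might infer that Appendix 2 authorizes randomizing such patients. It does not: it only fails to stop them.
- **Appendix 2 is treatment guidance.** Sections 6.4.3, 6.4.4 and 6.4.6 send the investigator there for dose adjustment, rescue and discontinuation, not for eligibility. That is fair for the management bands, which are not questioned. It does not cover two sentences that expressly concern the screening period, one of which is about whether to randomize.
- **The first sentence may have its own scope.** Criterion 10 tests values at the visits, whereas the withdrawal sentence could cover extra values between visits, confirmed on repeat. That reading is possible for the first sentence. It does not explain the second, which addresses the decision criterion 10 already settles at Visit 2. Criterion 10 says nothing about repeat testing, and that silence is not treated as a contradiction.
- **Harm needs a misreading.** This is a single-center trial, local tests supplement the central laboratory, and an investigator would have to pass over sections 4.2 and 5.2. This also stands, and it limits the weight of the point without removing the conflict.

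**Conclusion.** The inconsistency is real and does not depend on the unseen comparison sign. Appendix 2 prints a screening limit 0.3 mmol/L above the one that governs entry, which leaves 5.3 and 5.4 mmol/L open to misjudgement by anyone who takes the limit from the appendix. The conclusion rests on sections 4.2.1 and 4.2.2 giving priority to the entry criteria and, for the listed values, on one-decimal reporting.

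The size is small. Nobody is misclassified when criterion 10 is followed, the documents give no basis for a count of affected patients, and no endpoint, analysis or sample size changes. It is a minor correction.

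A reader might look for further proof elsewhere that 5.2 was intended, but the documents do not supply it. The Appendix 2 heading ("serum potassium greater than or equal to 5.3 mmol/L") sets the scope for managing hyperkalemia, and its first band starts above 5.3, so it does not show which screening limit was meant. The renal limits in Appendix 4 agree with criterion 8, but they are stated for the randomization period rather than screening and say nothing about potassium. Section 12 ("no authorized deviations are permitted") forbids departures from the protocol without saying which of two printed figures is right.

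**What to change.** In both screening sentences of Appendix 2, General principles, replace 5.5 mmol/L with above 5.2 mmol/L at Visit 1 or Visit 2, as in exclusion criterion 10. Write the number and the two visits out. A bare pointer to criterion 10 would also bring in its wording on Visits 3 and 4, where Appendix 2 manages raised potassium by monitoring, down-titration or interruption. Leave those post-randomization bands unchanged.

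The cost is two corrected sentences. No test, visit or analysis is added.

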#### **Corrective action for management of hyperkalemia**

##### **Serum potassium > 5.3 and less than or equal to 5.5 mmol/L**

- Confirm potassium concentration in a non-hemolyzed sample
- Reinforce low potassium diet and restriction of food/drinks with high potassium content (e.g. orange juice, melon, bananas, low-salt substitutes etc.)
- Review medical regimen (including dietary supplements and over-the-counter medications) for agents known to cause hyperkalemia. Consider reduction in dose or discontinuation of these agents:
  - Potassium-sparing diuretics (e.g. amiloride and triamterene) including in combination products with thiazide or loop diuretics
  - Potassium supplements, e.g., potassium chloride
  - Salt substitutes
  - Non-steroidal anti-inflammatory drugs (NSAIDs)
  - Cyclo-oxygenase-2 (COX-2) inhibitors
  - Trimethoprim and trimethoprim-containing combination products, such as Bactrim® and Septra® (trimethoprim/sulfamethoxazole fixed combination)
  - Herbal Supplements:
    - For example, Noni juice, alfalfa (*Medicago sativa*), dandelion (*Taraxacum officinale*), horsetail (*Equisetum arvense*), nettle (*Urtica dioica*), milkweed, lily of the valley, Siberian ginseng, hawthorn berries
- Repeat serum potassium measurement within 3 to 5 days
- If serum potassium remains  $> 5.3$  and  $\leq 5.5$  mmol/L, regularly monitor serum potassium levels to ensure stability (suggested once monthly)
- Consider down-titration of study medication, according to investigator's medical judgment.

**Serum potassium  $> 5.5$  and  $< 6.0$  mmol/L**

- Confirm potassium concentration in a non-hemolyzed sample
- Consider down-titration or temporarily discontinue study drug according to investigator medical judgment.
- Apply all measures outlined for serum potassium  $> 5.3$  and  $\leq 5.5$  mmol/L
- Repeat serum potassium measurement after 2-3 days
- If serum potassium  $< 5.5$  mmol/L, consider resumption of study drug at lower dose with repeat potassium within 5 days

**Serum potassium greater than or equal to 6.0 mmol/L**

- Immediately discontinue study drug
  - Confirm potassium concentration in a non-hemolyzed sample
  - Urgently evaluate patient and treat hyperkalemia as clinically indicated
  - Apply all measures outlined for serum potassium  $> 5.3$  and  $< 6.0$  mmol/L
- No resumption of study drug without individualized case discussion with and permission from his/her designee.

## **16 Appendix 3: Guidelines for the management of blood pressure Guidelines**

1. Investigator should monitor blood pressure closely
2. If symptomatic hypotension occurs:
  - a. Correct any treatable cause, e.g. hypovolemia
  - b. If hypotension persists, any antihypertensive drug and non-life saving drugs should be down-titrated or stopped first before down-titration of the study drug is considered
  - c. If hypotension persists, the study drug should be down-titrated or even temporarily withdrawn. The dose re-challenge and medications adjust guidelines described in Section 6.4.3 should be adhered to as much as possible.

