#### **4.2.4 Follow-up period**

##### **Visit 4 (Follow-up Visit)**

Follow-up visits are scheduled for Weeks 4, 12 and 24. Blood and urine samples are sent to a central laboratory for hematology, chemistry, and serum and urinary biomarkers. Professionals use Philips IE33 ultrasound system (Philips Medical System, Bothell, Washington, USA) for echocardiographic measurements. In addition to the protocol-required visits, patients may be seen at any time throughout the study at the discretion of the investigator to investigate or follow any new lab abnormalities or adverse events.

Monitoring of safety and tolerability will include: (1) hyperkalemia; (2) symptomatic hypotension; (3) increase in serum creatinine; (d) angioedema; and (e) adverse events and serious adverse events. If, in the opinion of the investigator, the patient cannot tolerate the target dose of study drug, the investigator should consider whether non-life saving medication (e.g., CCBs, nitrates,  $\alpha$ -blockers) can be reduced to rectify the situation before considering reducing the dose of the study drug to the lower dose level. The dose of background disease modifying drugs, such as  $\beta$ -blockers and mineralocorticoid receptor antagonists, should not be reduced to facilitate maintenance of study drug. If the situation is not rectified despite adjusting/discontinuing nonlife-saving medications or if adjusting non-life-saving concomitant medications is not possible, patients who no longer tolerate the target dose at any time during the course of the trial can be down-titrated to the lower dose level at the investigator's discretion (please refer to Figure 1 for dose levels available for titration). However, every attempt should be made to re-challenge the patients so that they are kept on the maximal tolerated dose of study drug for as long a duration as possible throughout the outpatient

dose titration and follow-up period of the trial. Please refer to Section 6.4.3 for a guidance on study drug dose adjustment.

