### **6.4.3 Permitted study drug dose adjustments and interruptions**

Every attempt should be made to maintain patients on the target study drug dose level for as long a duration as possible throughout the trial. If, however, in the opinion of the investigator, the patient does not tolerate the target dose of study drug (dose level 3), the investigator should consider whether non-life saving medication (e.g., CCBs, nitrates,  $\alpha$ -blockers) can be reduced to rectify the situation, before considering to reduce the dose of the study drug to the next lower dose level. If adjustment/elimination of

other non-life-saving HF medications is not possible or does not alleviate the side effects of concern, the investigator may down-titrate the dose of the study drug to the next lower level up to complete withdrawal of the study drug. The patient should be re-challenged with the higher dose when the investigator feels it is appropriate to do so per the directions provided below in this section. If needed, the study drug may be stopped completely, but the patient should continue to attend the study visits and be followed until the completion of the study. Ultimately the goal is to keep the patient on the highest study drug dose possible for as long as possible and to follow the patient in the study as long as possible.

Study drug dose level adjustments should mainly be based on overall safety and tolerability with special focus on a) hyperkalemia; b) symptomatic hypotension; and c) clinically significant decrease in eGFR/increase in serum creatinine (see Appendices 2, 3 and 4 for treatment guidelines for hyperkalemia, management of BP, and renal dysfunction, respectively).

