#### **6.4.4 Rescue medication**

Guidance on handling hyperkalemia, hypotension, and renal dysfunction are provided to investigators in Appendices 2, 3, and 4, respectively. Patients may receive other ACEIs and/or ARBs during the study ONLY if the study medication has been discontinued either temporarily or permanently.

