##### **Secondary prevention drugs for coronary heart disease and other cardiovascular medications**

The patient should be on an optimal medical regimen of background AMI medications. Medications after PCI also include: dual antiplatelet, statins, beta blockers and so on. The use of mineralocorticoid receptor antagonist (MRA), diuretics and inotropes according to the patient's condition. Every effort should be made to keep the dose level of these background, life-saving AMI medications stable throughout the entire study. However, if the patient's condition warrants a change in any of these medications, it is allowed at the discretion of the study investigator.

Diuretics may be used and may be adjusted throughout the length of the study at the discretion of the investigator.

If a patient experiences any adverse events that may be contributed to the study drug, other Secondary prevention drugs for coronary heart disease, or other CV medications, the investigator should adjust non-life saving medications (e.g., CCBs, nitrates, a-blockers, and diuretics) first in an attempt to alleviate the adverse events.

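### Appendix 3 lists any antihypertensive for reduction before study drug in persistent hypotension, without the beta-blocker and MRA exception stated in the synopsis and Section 4.2.4

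*Protocol*

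**What the plan says.** Appendix 3 first asks the site to correct any treatable cause of symptomatic hypotension. If hypotension persists, step 2b says that "any antihypertensive drug and non-life saving drugs should be down-titrated or stopped first before down-titration of the study drug is considered". If it still persists, step 2c allows study drug to be reduced or temporarily withdrawn, and adds that the "medications adjust guidelines described in Section 6.4.3 should be adhered to as much as possible".

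The synopsis (Visit 4) and Section 4.2.4 carry the same paragraph. When the target dose is not tolerated, non-life-saving drugs are considered for reduction first, with CCBs, nitrates and alpha-blockers as examples. The paragraph then protects background disease-modifying drugs: beta-blockers and "mineralocorticoid receptor antagonists, should not be reduced to facilitate maintenance of study drug".

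Section 6.4.3 sets the same order. If the patient "does not tolerate the target dose of study drug (dose level 3), the investigator should consider whether non-life saving medication" can be reduced before study drug is lowered. It does not repeat the protection for beta-blockers and MRAs.

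Section 6.4.5 describes background therapy ("Medications after PCI also include: dual antiplatelet, statins, beta blockers and so on"), adds MRAs according to the patient's condition, and asks that the doses of these drugs be kept stable. For adverse events, "the investigator should adjust non-life saving medications (e.g., CCBs, nitrates, a-blockers, and diuretics) first in an attempt to alleviate the adverse events". It also leaves room for judgment: if the patient's "condition warrants a change in any of these medications, it is allowed at the discretion of the study investigator".

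Section 6.4.4 points the site to the appendices: "Guidance on handling hyperkalemia, hypotension, and renal dysfunction are provided to investigators in Appendices 2, 3, and 4, respectively". Sections 6.4.3 and 6.4.6 make the same referral.

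**The concern.** Step 2b names two groups joined by 'and': antihypertensives of any kind, and non-life-saving drugs. The first group has no qualifier. Beta-blockers and MRAs lower blood pressure, so a clinician working from the appendix would reasonably include them. The step then tells the site to do what Section 4.2.4 says not to do, namely reduce these drugs so that study drug can be kept.

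What is at stake is patient safety and uniform conduct. The patients have just had an anterior STEMI, and the protocol itself treats beta-blockers as standard medication after PCI. The situation is foreseeable. Hypotension is a named safety outcome (Sections 1 and 10.5), and Section 4.2.2 requires 6 hours of monitoring for it after the first sacubitril/valsartan dose. Section 12 permits no authorised deviations, so a site that follows one text may depart from the other.

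**Working it through.** No arithmetic beyond a count of the text applies: the point rests on no rate, effect size or sample size. The five places that say what is reduced before study drug, or first for an adverse event, compare as follows.

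| Place in protocol | Reduced first | Example classes given? | Beta-blockers and MRAs protected by name? |
|---|---|---|---|
| Synopsis, Visit 4 | Non-life-saving drugs | Yes | Yes |
| Section 4.2.4 | Non-life-saving drugs | Yes | Yes |
| Section 6.4.3 | Non-life-saving drugs | Yes | No |
| Section 6.4.5 | Non-life-saving drugs | Yes | No, but background doses are to be kept stable, with discretion |
| Appendix 3, step 2b | Any antihypertensive, and non-life-saving drugs | No | No |

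- **Limited to non-life-saving drugs:** 4 of 5 places. The synopsis and Section 4.2.4 repeat one paragraph, so counted as distinct statements this is 3 of 4.
- **Protection by name:** 2 of 5 places, or 1 of 4 distinct statements.
- **Protection in Section 6.4.3 or Appendix 3:** 0 of 2.

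**Can the wording of step 2b be squared with the rest?** Only if 'antihypertensive' is read narrowly, for example as CCBs and alpha-blockers. Those are already examples of non-life-saving drugs elsewhere in the protocol, so on that reading the extra phrase adds nothing. Appendix 3 gives no examples and no qualifier to signal it.

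**Does the cross-reference repair it?** Follow the route a site would take. Section 6.4.3 sends it to Appendix 3 for blood pressure. Step 2c of Appendix 3 sends it back to Section 6.4.3. Neither text holds the beta-blocker and MRA rule, so a reader can follow this route in full without meeting it. The return reference also comes only after step 2b has been carried out, and it binds only as far as possible.

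**Does the discretion in Section 6.4.5 repair it?** No. It allows a change to background drugs when the patient's condition calls for one. Step 2b makes reduction a default step that comes before any reduction of study drug.

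**The case against.** The strongest reply is that the conflict depends on one reading. The protocol calls beta-blockers and MRAs disease-modifying or life-saving background drugs and never antihypertensives. The classes it repeatedly offers for early reduction are CCBs, nitrates and alpha-blockers. An explicit rule naming two classes would normally govern a general phrase in a short appendix. Step 2c also points to Section 6.4.3, whose rule on concomitant drugs is the restricted one. In addition, persistent symptomatic hypotension can itself be a condition that warrants changing a background drug under Section 6.4.5, so a site that lowers a beta-blocker may be within the protocol. Some variation between investigators is intended, and it would remain after the wording is fixed. Finally, no frequency or effect on an endpoint can be shown.

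Much of this stands as mitigation. The narrower reading is available and may be what was meant. The Section 6.4.5 discretion is real, so not every reduction of a beta-blocker or MRA would breach the protocol. The text count is not a measure of harm, and nothing can be said about imbalance between arms, because no hypotension rates are given.

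It does not remove the defect. The specific rule can govern only if the reader finds it, and the hypotension guidance does not lead there. Discretion to change a drug because the patient needs it differs from an instruction to reduce it before study drug is considered.

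**Conclusion.** The concern holds as a conflict in the order of steps. Followed literally, step 2b of Appendix 3 has beta-blockers and MRAs reduced or stopped before study drug, contrary to the synopsis and Section 4.2.4 and out of line with Sections 6.4.3 and 6.4.5. This assumes the ordinary meaning of 'any antihypertensive'. Under the narrower meaning the texts agree, but the appendix does not say that this is intended.

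The size in patients is unknown, since the protocol gives neither a hypotension rate nor a rate of beta-blocker or MRA use. The point changes no endpoint definition, analysis or sample size. It should still be corrected, because it concerns a safety step that is likely to be used and that gives the wrong action if taken at its word.

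**What to change.** Replace step 2b of Appendix 3 with wording such as: *Reduce or stop non-life-saving drugs that lower blood pressure (for example CCBs, nitrates, alpha-blockers, diuretics) first. Do not reduce beta-blockers or MRAs in order to keep the patient on study drug (see Section 4.2.4). Changes that the patient's condition itself requires remain at the investigator's discretion under Section 6.4.5.*

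Repeat the sentence on beta-blockers and MRAs in Section 6.4.3, so that a site meets it whichever of the two texts it opens. The last sentence leaves clinical judgment in place; what changes is the default order.

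The cost is one reworded appendix step and one added sentence in Section 6.4.3, with no extra visits, data or patients. If the protocol is already in force, Section 12 requires the change to go through as an amendment with ethics committee approval.
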